#### **5.4.2.5. Concomitant Medication**

Medications will be coded using the GSKDRUG dictionary.

### **5.5. Analysis of RTI**

#### **5.5.1. Analysis of RTI planned in the protocol**

The analysis will be performed on the ES.

Any RTI episode for which a visit for the assessment of potential RSV-RTI has been performed (with nasal/throat swab sampling) will be described in detail in a listing. This will present the results of the qRT-PCR performed on the nasal swab collected by the subject and on the nasal/throat swab collected by an appropriately qualified person (i.e., medical or nursing) at the assessment visit.

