## RSV molecular biology

For identified RTI cases under active or passive surveillance, the potential RSV infection will be assessed by quantitative reverse transcription PCR (qRT-PCR) testing of swabs (see [Table 10](#)).

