### 8.6.1. Active surveillance

During the RSV seasons, study participants will be contacted by the investigator/study staff every 2 weeks to identify if they experience RTI symptoms (i.e., cough, runny nose, fever [ $\geq 37.5^{\circ}\text{C}$ ] or difficulty to breathe). A template script will be provided separately by GSK.

In case of RTI symptoms (at least 3; see Section [8.6.3](#)) reported by the subject, the subject will be asked to collect a nasal swab at home ideally within 48 hours after the start of symptoms. An assessment visit for nasal and throat swab specimen collection by qualified staff from the study team will be scheduled. The assessment visit should take place as soon as possible after the start of symptoms (ideally within 48 hours, but no later than 7 days). Episodes should be treated accordingly to local standard of care.

In the event that it is not possible to schedule an assessment visit, the assessment visit page of the eCRF should be filled in as completely as possible using available medical records.

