### 8.6.2. Passive surveillance

Study participants will be instructed to contact the investigator/study staff in case of RTI symptoms during the RSV seasons (e.g., cough, runny nose, fever [ $\geq 37.5^{\circ}\text{C}$ ] or difficulty to breathe).

In case of RTI symptoms (at least 3) reported by the subject, the subject will be asked to collect a nasal swab at home within 48 hours after the start of symptoms and contact the investigator/study staff, who will schedule an assessment visit for nasal and throat swab specimen collection by qualified staff from the study team. The assessment visit should take place as soon as possible after the start of symptoms (ideally within 48 hours, but no later than 7 days). Episodes should be treated according to local standard of care.

In the event that it is not possible to schedule an assessment visit, the assessment visit page of the eCRF should be filled in as completely as possible using available medical records.

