### **8.6.3. Assessment Visit for potential RSV-RTI**

The purpose of the Assessment Visit for potential RSV-RTI is to objectively document signs and symptoms (e.g., cough, runny nose, fever [ $\geq 37.5^{\circ}\text{C}$ ] or difficulty to breathe) by an appropriately qualified person (i.e., medical or nursing) and to take nasal and throat swabs for detection of RSV infection. The visit should take place as soon as possible after the start of symptoms (ideally within 48 hours, but no later than 7 days).

- Assessment visits may take place in the study participant's home, the investigator's clinical facility or a medical facility as appropriate to the circumstances in the judgment of the investigator.
- If the reported symptoms are already of a level of severity that urgent care is indicated, the study participant should be redirected to the proper location to receive this care (e.g. Emergency Room) and an assessment visit could be scheduled to take place there at a suitable time.
- For self-collection as well as staff-collection, swabs for analysis at sponsor laboratory should be collected when subjects show at least 3 of the following signs/symptoms:
  - Nasal congestion,
  - Sore throat,
  - Earache,
  - New or worsening cough,
  - New or worsening sputum,
  - Dyspnea,
  - Rhinorrhea,
  - Wheezing (whistling, musical or puffing sound made on exhalation) or worsening of wheezing,
  - Rales (crackles),
  - Rhonchi (sound with musical pitch during inspiration or expiration),
  - Fever (temperature of  $\geq 37.5^{\circ}\text{C}$ ) or feeling feverish.

- During the assessment visit, the investigator/study staff will evaluate the clinical signs and symptoms of the RTI and measure the subject's resting vital signs (systolic/diastolic blood pressure, pulse oximetry, heart rate, respiratory rate after at least 10 minutes of rest) and temperature. RTI symptoms include, but may not be limited to, the following:
  - **Upper respiratory symptoms:** nasal congestion, sore throat, rhinorrhea, earache.
  - **Lower respiratory symptoms:** new or worsening cough, new or worsening of sputum production, dyspnea, wheezing or worsening of wheezing, rales (crackles), rhonchi.
  - **Systemic symptoms:** myalgia, arthralgia, fatigue, headache, decreased appetite, feverishness, pain (localized at chest or abdomen at respiration).
- Signs and symptoms, resting vital signs, temperature and onset date of first symptom should be recorded within the RTI episode screen in the eCRF.

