### 10.3.4. Other analyses

#### 10.3.4.1. Analysis of RTI

The analysis will be performed on the ES.

Endpoint	Statistical Analysis Methods
Primary	N/A
Secondary/Tertiary	A listing of RTI cases and their respective viral load results assessed by qRT-PCR will be provided by group.

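### SAP 5.5.1 limits the protocol-planned RTI listing to episodes with an assessment visit and staff swab, and SAP section 8 declares no change

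*SAP*

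**What the plan says.** Protocol 10.3.4.1 gives the whole RTI analysis in one row, shared by the secondary and tertiary endpoints and run on the Exposed Set: "A listing of RTI cases and their respective viral load results assessed by qRT-PCR will be provided by group". No visit or staff-collected swab is required for a case to be listed.

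SAP 5.5.1 describes the corresponding listing. It covers "Any RTI episode for which a visit for the assessment of potential RSV-RTI has been performed (with nasal/throat swab sampling", and for those episodes shows the qRT-PCR results of both the subject's own swab and the staff swab. It does not say that the listing is by group. SAP 5.5.2 adds a description of information gathered at the visit, split into RSV and non-RSV episodes according to the visit swab alone. SAP section 8, on changes from planned analyses, contains only the entry NA.

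Protocol 8.6.1 provides for RTI episodes without a visit: "In the event that it is not possible to schedule an assessment visit, the assessment visit page of the eCRF should be filled in" from available medical records. Protocol 8.6.2 repeats the provision for passive surveillance ("In the event that it is not possible to schedule an assessment visit"). Protocol 8.6.3 gives each RTI episode its own number and section in the eCRF.

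**The concern.** The SAP adds an entry condition to an analysis that it attributes to the protocol, and it records no change. The episodes that fail the condition are ones that the protocol expects and tells sites to record.

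The condition fits the secondary RTI endpoint, which is defined on swabs taken at the assessment visit. It does not fit the tertiary endpoint, RSV-associated RTI in self-collected nasal swabs, which carries no visit requirement in Protocol section 4 or SAP section 2. The protocol's single listing serves both. A subject with a tested, RSV-positive home swab and no staff swab would meet the tertiary endpoint and yet be missing from the listing meant to report it.

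At stake is the completeness, by group, of a descriptive listing in a trial of about 20 subjects per group. No hypothesis test, sample-size figure or safety conclusion depends on it.

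**Working it through.** The documents give no figure for this point, and the check is a comparison of texts.

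1. **Scope planned in the protocol.** Section 10.3.4.1 lists RTI cases with their viral load results, by group, for the secondary and tertiary endpoints. The part of section 8.4.3 on RSV molecular biology is equally broad: "For identified RTI cases under active or passive surveillance, the potential RSV infection will be assessed by quantitative reverse transcription PCR". The footnote to Table 13 says that qRT-PCR is run on every specimen, and the table includes home swabs.

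2. **Scope in the SAP.** Section 5.5.1 requires both a performed visit and nasal/throat sampling. The SAP text describes no other RTI listing. Section 5.5.2 does not widen the scope, because it concerns information collected at the visit.

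3. **Each kind of episode under both texts:**

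| Episode | Recorded in eCRF | Protocol 10.3.4.1 | SAP 5.5.1 | Endpoint it can meet |
|---|---|---|---|---|
| Visit and staff swab, with or without home swab | Yes | Listed | Listed, with home-swab result if there is one | Secondary; tertiary if the home swab is positive |
| No visit, home swab tested | Yes | Listed | Not listed | Tertiary if the home swab is positive |
| No visit, no swab | Yes | Listed as an RTI case, without a result | Not listed | None |

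The second and third rows are where the two texts differ. Only the second can hide an endpoint event, and that event is tertiary.

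4. **Effect on the other endpoints.** An episode without a visit swab cannot meet the secondary RTI endpoint, so the SAP condition removes no secondary event. The primary endpoint concerns adverse events and laboratory abnormalities and does not use this listing.

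5. **Whether the change is declared.** SAP section 8 says NA. Protocol 10.3 requires changes to the statistical plan to be described and justified in the final study report. A restriction presented as the protocol's own analysis is easily overlooked when that report is written.

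6. **How many episodes.** The documents give no rate of RTI episodes, of missed visits, or of home swabs tested without a visit. The number cannot be derived. Two provisions suggest that the second row is rare: Table 7 gives the assessment visit as the timepoint for the home swab, and section 8.4.2.2 has staff swabs taken at the assessment visit without further condition.

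**The case against.** The strongest reply is that the SAP only makes the protocol operational. Section 10.3.4.1 does not define an RTI case, and it pairs cases with viral load results, so a listing of episodes that have specimens is a reasonable reading. On that reading NA in section 8 is consistent, and most of the added rows would carry no PCR result. The protocol places the duty to report changes in the final study report and does not name SAP section 8. The planned outputs are itemised in a separate TFL table of contents (SAP 10.2), which was not available, so a fuller RTI listing there cannot be excluded. Tertiary results may also be reported later in annexes.

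Much of this stands. It limits the point to the SAP text and keeps it minor. It does not remove the mismatch: the SAP does not present its condition as a definition, and the condition fits only one of the two endpoints that the listing serves.

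A reader might infer two stronger claims, and the documents support neither.

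- **A visit without a staff swab.** Protocol 8.6.3 says that "swabs for analysis at sponsor laboratory should be collected when subjects show at least 3 of the following signs/symptoms", for self-collection and staff collection alike. One might conclude that a subject whose symptoms have eased by the visit would have a home swab but no staff swab. Section 8.4.2.2 has both swabs collected at the visit without a symptom count, and 8.6.3 names swab collection as a purpose of the visit. The three-symptom rule can equally be read as the trigger for the episode.
- **A large share of episodes lost.** Under 8.6.1, "study participants will be contacted by the investigator/study staff every 2 weeks to identify if they experience RTI symptoms", and the visit is due "ideally within 48 hours, but no later than 7 days" after onset. One could calculate how often an episode found only at a contact is already past the limit. That would measure visits missing a protocol window. SAP 5.5.1 has no such window, so a late visit with a swab is still listed. The calculation would also need an onset distribution and a share of episodes found only at contacts, and the documents give neither.

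**Conclusion.** The point holds as a minor inconsistency between the SAP and the protocol, with moderate confidence. SAP 5.5.1 restricts the RTI listing to episodes with a performed visit and nasal/throat sampling and omits the by-group presentation. Protocol 10.3.4.1 has no such restriction, Protocol 8.6.1 and 8.6.2 foresee episodes without a visit, and SAP section 8 reports no change.

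The conclusion rests on a literal reading of SAP 5.5.1 and on RTI cases in 10.3.4.1 meaning episodes identified under surveillance, as 8.4.3 suggests. It would fall away if the TFL table of contents already holds a by-group listing of all recorded episodes; the SAP wording would then only need aligning.

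The size is unknown and probably small. It would be wrong to say that self-swab results go unreported in general, since SAP 5.5.1 shows them for every episode it lists, or that data are lost, since the omitted episodes remain in the eCRF.

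**What to change.** In SAP 5.5.1, state that every RTI episode recorded in the eCRF will be listed by treatment group, with its visit status, its swab status and each available qRT-PCR result, self-collected and staff-collected. Episodes with a positive self-swab can then be identified for the tertiary endpoint whether or not a staff swab exists. The secondary endpoint definition does not change.

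If the restriction is intended, keep it, but declare it in SAP section 8 with the reason, and say how self-swab-positive episodes without a staff swab will be reported.

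The cost is one sentence in the SAP and minor programming. No new data are collected. Some rows will show no PCR result.

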#### **5.5.2. Additional considerations**

Information collected at assessment visit will be further described for RSV RTI episodes versus Non-RSV RTI episodes. An RTI episode will be considered as associated to RSV when the qRT-PCR test performed on nasal/throat swabs collected at assessment visit is positive. It will include: vital signs, clinical signs and symptoms, self-collected nasal swab result, medically attended visit and SAE related to the episode.

## **6. ANALYSIS INTERPRETATION**

The analyses will be descriptive with the aim to characterize the safety/reactogenicity and immunogenicity of the RSV group with respect to the placebo.

## **7. CONDUCT OF ANALYSES**

### **7.1. Sequence of analyses**

The following analyses will be performed stepwise:

- A first analysis will be performed on all data available and as clean as possible, when data for at least primary and secondary endpoints up to Day 91 are available (except for the occurrence of RSV RTI). This analysis will be considered as final for those endpoints. A statistical report will be written.

At this point, the statistician will be unblinded (i.e., individual subject treatment assignments will be available), but no individual listings will be provided to the study team. Given that summary safety results may unblind some specific subjects, the study will be considered as single-blind from this point onwards, with subjects remaining blinded up to study end (Month 14). The investigators will not be provided with the individual data listings or with the randomization listings until the end of study analysis.

- The end of study analysis will be performed when all data for primary and secondary endpoints up to study conclusion are available (Month 14). Individual listings will only be provided at this stage. An integrated clinical study report containing all available data will be written and made available to the investigators.

The final study report will contain at least the final analyses of all primary and secondary endpoints. If the data for tertiary endpoints become available at a later stage, (an) additional analysis/ analyses will be performed. These analyses will be documented in annex(es) to the study report and will be made available to the investigators at that time.

Description	Analysis ID	Disclosure Purpose (CTRS=public posting, SR=study report, internal)	Reference for TFL TOC
End of study analysis	E1_01	CTRS, SR	See column 5 in TFL TOC
Analysis up to Day 91	E1_02	Internal	See column 5 in TFL TOC

## 7.2. Statistical considerations for interim analyses

All analyses will be conducted on final data (as clean as possible) and therefore no statistical adjustment for interim analyses is required.

## 8. CHANGES FROM PLANNED ANALYSES

NA

## 9. NON-STANDARD DATA DERIVATION RULES AND STATISTICAL METHODS

The following sections describe additional derivation rules and statistical methods which are not presented in section 10.1.

### 9.1. Handling of missing data

#### 9.1.1. Dates

When partially completed dates (i.e. with missing day or month) are used in calculations, the following rules will be applied:

- Adverse event start dates with missing day:
  - If the month is not the same as the vaccine dose, then the imputed start date will be the 1st of the month.

- If the event starts in the same month as the vaccine dose, the flag indicating if the event occurred before or after vaccination (AE.AESTRTPT) will be used to complete the date. If ‘after vaccination’ is selected, the imputed start date will match the vaccine dose given during that month. If ‘before vaccination’ is selected, the imputed date will be one day before the vaccine dose given during that month.
- Adverse event start dates with missing day and month:
  - If the year is not the same as the vaccine dose, then the imputed start date will be the 1st of January.
  - If the event starts in the same year as the vaccine dose, the flag indicating if the event occurred before or after vaccination (AE.AESTRTPT) will be used to complete the date. If ‘after vaccination’ is selected, the imputed start date will match the first vaccine dose given during that year. If ‘before vaccination’ is selected, the imputed date will be one day before the first vaccine dose given during that year.
- Adverse event end dates with missing day: the imputed end date will be the last day of the month (30 or 31) or the study conclusion date whichever comes first.
- Adverse event end dates with missing day and month: the imputed end date will be the last day of the year (31st of December) or the study conclusion date whichever comes first.

All other cases of incomplete AE or concomitant medication/vaccination start date will follow the standard rules above.

## 10. ANNEXES

### 10.1. Business rules for standard data derivations and statistical methods

This section contains GSK Vaccines' standard rules for data display and derivation for clinical and epidemiological studies. These rules will be applied along with those detailed in section 9 (additional study-specific rules).

#### 10.1.1. Attributing events to vaccine doses

The dose relative to an event is the most recent study dose given to a subject prior to the start of a given event. For example, if the start date of an adverse event is between Dose 1 and Dose 2, the relative dose will be Dose 1.

If an event starts on the same day as a study dose, the relative dose will be derived from the additional information provided in the CRF using the contents of the flag indicating if the event occurred before or after vaccination. If 'after vaccination' is selected, the relative dose for the event will be the one administered on the start day of the event. If 'before vaccination' is selected, the relative dose for the event will be the dose prior to this one.

#### 10.1.2. Handling of missing data

##### 10.1.2.1. Dates

When partially completed dates (i.e. with missing day or month) are used in calculations, the following standard rules will be applied:

- A missing day will be replaced by 15
- A missing day and month will be replaced by June 30th.

See also exceptions in section 9.1.

##### 10.1.2.2. Laboratory data

Missing laboratory results (including immunological data) will not be replaced.

##### 10.1.2.3. Daily recording of solicited adverse events

###### 10.1.2.3.1. Studies with electronic diaries

For studies using electronic diaries for the collection of solicited adverse events, a solicited adverse event will be considered present only when a daily recording of grade 1 or more is present.

##### 10.1.2.4. Unsolicited adverse events

Missing severity, relationship with study vaccine, and outcome of unsolicited adverse events will not be replaced and will appear as 'UNKNOWN' in all statistical output.

### 10.1.3. Data derivation

#### 10.1.3.1. Age at vaccination in years

When age at vaccination is to be displayed in years, it will be calculated as the number of complete calendar years between the date of birth and the date of vaccination. For example:

DOB = SEP1983, Date of vaccination = 14SEP2018

-> Derived DOB=15SEP1983 and derived Age = 34 years

DOB = SEP1983, Date of vaccination = 15SEP2018

-> Derived DOB=15SEP1983 and derived Age = 35 years

#### 10.1.3.2. Numerical serology results

Numerical serology results will be derived from the content of IS.ISORRES in the SDTM dataset. For assays with a specific cut-off, the following derivation rules apply:

IS.ISORRES	Derived value
“NEG”, “-”, or “(−)”	cut-off/2
“POS”, “+”, or “(+)”	cut-off
“< value” and value is <= assay cut-off	cut-off/2
“< value” and value is > assay cut-off	value
“> value” and value is < assay cut-off	cut-off/2
“> value” and value is >= assay cut-off	value
“value” and value is < cut-off	cut-off/2
“value” and value is >= cut-off and value is <=ULOQ	value
“value” and value is > ULOQ	ULOQ
All other cases	missing

#### 10.1.3.3. Geometric mean titres (GMTs) and concentrations (GMCs)

Geometric Mean Titre (GMT) or Concentration (GMC) calculations are performed by taking the inverse logarithm of the mean of the log titer or concentration transformations. Antibody titer or concentrations below the cut-off of the assay will be given an arbitrary value of half the cut-off of the assay for the purpose of GMT/GMC calculation. The cut-off value is defined by the laboratory before the analysis and is described in the protocol.

#### 10.1.3.4. Onset day

The onset day for an event (e.g. AE, medication, vaccination) is the number of days between the last study vaccination and the start date of the event. This is 1 for an event occurring on the same day as a vaccination (and reported as starting after vaccination).

**10.1.3.5. Duration of events**

The duration of an event with a start and end date will be the number of days between the start and end dates plus one day, i.e. an event that starts on 03MAR2018 and ends on 12MAR2018 has a duration of 10 days.

The duration of solicited events will be calculated as the sum of the individual days with the adverse event reported at grade 1 or higher during the solicited adverse event period.

**10.1.3.6. Counting rules for combining solicited and unsolicited adverse events**

For output combining solicited and unsolicited adverse events, all serious adverse events will be considered general events since the administration site flag is not included in the expedited adverse event CRF pages.

Multiple events with the same preferred term which start on the same day are counted as only one occurrence.

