### **8.3.13. Recording of AEs and SAEs**

Solicited AEs will be recorded by the subjects or their designee in the eDiaries.

Non-serious unsolicited AEs will be recorded by the investigator in the Non-Serious Adverse Event section of the eCRF.

Any serious adverse event (SAE), (solicited or unsolicited) will be recorded by the investigator in the Expedited Adverse Event report in the eCRF.

Refer to Section [12.5.7](#) for the detailed procedures for the investigator to record AEs and SAEs. Refer to Section [12.5.8](#) for guidelines and how to report SAE reports to GSK.

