**Table 17 Study holding rules identifiable by the investigator**

Holding Rule	Event	Number of subjects
1a	Death or any life-threatening SAE	≥ 1
1b	Any non-life-threatening SAE that cannot reasonably be attributed to a cause other than vaccination (non-life-threatening related SAEs)	≥ 1
1c	Any local or general solicited AE leading to hospitalization , or fever > 40°C that cannot reasonably be attributed to a cause other than vaccination, or necrosis at the injection site, within the 7-day (Day 1-7) post-vaccination period	≥ 1

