- Timely completion of the eDiary on a daily basis is a critical component to study participation.
- The eDiary will allow certain time windows for completion of each day's observations.
- The eDiary employs the use of audio-visual alarms to ensure timely completion of data entry.
- The trained and assigned user of the eDiary must not share access codes with anyone.
- A helpdesk will be provisioned for users of eDiary in case of technical issues, though it must be stressed that the Helpdesk is not a replacement for normal medical care and no medical issues can be discussed with the agents.
- The eDiary itself must never be considered a substitute for direct medical care and any concerns must be communicated to site staff as soon as possible.
- Any new safety information reported during the safety follow-up phone call or site visits (including a solicited adverse event) cannot be entered into the eDiary. Such information must be described in the source documents as a verbally-reported event. Any adverse event reported in this fashion must be described as an unsolicited adverse event and therefore entered into the eCRF.

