#### **12.5.7.1. Time period for detecting and recording adverse events and serious adverse events**

All solicited AEs during 7 days following administration of each dose of study vaccine (the day of vaccination and 6 subsequent days) must be recorded in the eDiary, irrespective of intensity or whether or not they are considered vaccination-related.

All unsolicited AEs during 30 days following administration of each dose of study vaccine (the day of vaccination and 29 subsequent days) recorded by the subjects on their paper diary cards or reported orally must be recorded into the appropriate section of the eCRF, irrespective of intensity or whether or not they are considered vaccination-related.

The time period for collecting and recording SAEs will begin at the first receipt of study vaccine and will end 12 months following administration of the last dose of study vaccine for each subject. See Section [12.5.8](#) for instructions on reporting of SAEs to GSK.

All AEs/SAEs leading to withdrawal from the study will be collected and recorded from the time of the first receipt of study vaccine.

In addition to the above-mentioned reporting requirements and in order to fulfil international reporting obligations, SAEs that are related to study participation (i.e. protocol-mandated procedures, invasive tests, a change from existing therapy) or are related to a concurrent GSK medication/vaccine will be collected and recorded from the time the subject consents to participate in the study until she/he is discharged from the study.

The time period for collecting and recording of pIMDs will begin at the first receipt of study vaccine and will end 12 months following administration of the last dose of study vaccine. See section [12.5.8.4](#) for instructions on reporting of pIMDs.

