### **5.4.1. Analysis of safety and reactogenicity planned in the protocol**

- The percentage of subjects with at least one local AE (solicited and unsolicited), with at least one general AE (solicited and unsolicited) and with any AE during the 7-day or 30-day follow-up period will be tabulated with exact 95% confidence interval (CI) after each dose and overall. The same computations will be done for Grade 3 AEs, for any AEs considered related to vaccination, for Grade 3 AEs considered related to vaccination and for Grade 3 non-serious AEs.
- The percentage of subjects with any AE (solicited and unsolicited) resulting in a medically attended visit during the 30-day follow-up period will also be tabulated after each dose and overall.
- The percentage of subjects reporting each individual solicited local AE (any grade and Grade 3) and solicited general AE (any grade, Grade 3, any related and Grade 3 related) during the 7-day follow-up period (i.e., on the day of vaccination and 6 subsequent days) will be tabulated for each group after each dose and overall.
- For fever, the number and percentage of subjects reporting fever by half degree (°C) cumulative increments during the 7-day follow-up period (i.e., on the day of vaccination and 6 subsequent days) will be tabulated for each group after each dose and overall. Similar tabulations will be performed for any fever with a causal relationship to vaccination and for Grade 3 ( $> 39.0^{\circ}\text{C}$ ) causally related fever. In addition, the prevalence of any and Grade 3 fever will be presented graphically over time after each vaccination.
- For each group and for each hematology and biochemistry parameter:
  - i. The percentage of subjects having hematology and biochemistry results below or above the laboratory normal ranges will be tabulated by time point.
  - ii. The summary of grading post-vaccination will be tabulated versus baseline. Grades will be based on the FDA Guidance for Industry “Toxicity Grading Scale for Healthy Adults and Adolescent Volunteers Enrolled in Preventive Vaccine Clinical Trials”, see Protocol Section 12.7 The laboratory parameters not included on FDA Toxicity Grading Scale will not be graded.

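### Counting every SAE as a general event can move a serious injection-site reaction known only from the expedited report out of the local AE rows of the combined safety table

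*SAP*

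**What the plan says.** The counting rule is in SAP 10.1.3.6, among the sponsor's standard derivation rules. For combined outputs, "all serious adverse events will be considered general events since the administration site flag is not included in the expedited adverse event CRF pages". The reason given is the layout of a form, not a clinical argument.

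The table it reaches is the first item of SAP 5.4.1: "The percentage of subjects with at least one local AE (solicited and unsolicited), with at least one general AE (solicited and unsolicited"), with exact 95% CIs, for the 7-day or 30-day period, after each dose and overall. It is repeated for Grade 3, related, Grade 3 related and Grade 3 non-serious events. Protocol 10.3.2 describes the same table under the primary endpoint and makes no exception for SAEs. SAP section 8 lists no change from the planned analyses.

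Three recording rules decide which events are affected:

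- Protocol 8.3.13: "Any serious adverse event (SAE), (solicited or unsolicited) will be recorded by the investigator in the Expedited Adverse Event report in the eCRF". This is the form without the site flag.
- Protocol 12.5.7.1: solicited events in the 7-day window "must be recorded in the eDiary, irrespective of intensity or whether or not they are considered vaccination-related". SAP 10.1.2.3.1 then counts them from the diary: "a solicited adverse event will be considered present only when a daily recording of grade 1 or more is present".
- Protocol 12.5.7, on events told to staff at a visit or by telephone, which cannot go into the eDiary: "Any adverse event reported in this fashion must be described as an unsolicited adverse event and therefore entered into the eCRF".

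**The concern.** The protocol defines the local row as solicited plus unsolicited local events, serious or not. The SAP rule narrows it: a local event that becomes serious, and has no diary record, changes category because a flag is missing from the expedited page.

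The protocol foresees such events. Holding rule 1c in Table 17 names a local solicited AE leading to hospitalization and also necrosis "at the injection site, within the 7-day (Day 1-7) post-vaccination period". Only pain, redness and swelling are solicited locally (Table 23), so necrosis is not a diary item.

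At stake is the accuracy of the local and general split for a newly tested adjuvanted vaccine, above all in the Grade 3 local cells, where counts are likely to be small. The local figure may be too low, the general figure too high, or both.

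**Working it through.** **1. Which serious local events change row?**

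| Serious injection-site event | Where recorded | Row in the combined table |
|---|---|---|
| Pain, redness or swelling, Days 1–7, entered in the eDiary | eDiary and expedited report | Local (diary) and possibly also general (SAE) |
| Same symptoms, Days 1–7, reported only verbally | Expedited report | General only |
| Same symptoms, onset after the 7-day window (unsolicited under Protocol 12.5.4) | Expedited report | General only |
| Other local event, such as serious necrosis | Expedited report | General only |

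The first line is left open. SAP 10.1.3.6 merges events with the same preferred term and the same start day into one occurrence. It does not say whether that occurrence is local or general, and it does not cover records that differ in term or start date.

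**2. The plan's own figures for 20 subjects per group (Protocol 10.1.1).**

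Chance of at least one event = 1 − (1 − p)^20.

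- p = 7.8%: 80.3% (plan: 80%).
- p = 10.9%: 90.1% (plan: 90%).

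The Clopper-Pearson limits reproduce Table 19 to two decimals. For 0/20 the upper limit is 1 − 0.025^(1/20) = 16.84%. For 1/20 the lower limit is 1 − 0.975^(1/20) = 0.13% and the upper limit, from the beta quantile, is 24.87%.

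**3. Size of the shift.**

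The table counts subjects with at least one event, so one subject is worth 1/20 = 5 percentage points. Take a Grade 3 local cell in which the only contributor is a Grade 3 SAE known solely from the expedited report:

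- SAE counted as local: 1/20 = 5% (0.13–24.87%).
- SAE counted as general under the rule: 0/20 = 0% (0.00–16.84%).

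If the subject has another qualifying local record in that cell, the change is 0. A subject whose diary shows only Grade 1 or 2 pain stays in the any-grade local row but drops out of the Grade 3 local row. The matching general cell rises by 5 points only if the subject has no other general AE there.

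**4. How often could this arise?**

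The documents give no rate for serious injection-site reactions. Assuming a range of 0.1% to 5% per subject, the chance of at least one in a group of 20 is:

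| Assumed rate | 1 − (1 − p)^20 |
|---|---|
| 0.1% | 2.0% |
| 0.5% | 9.5% |
| 1% | 18.2% |
| 5% | 64.2% |

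If half of those subjects have no other local record in the cell (also an assumption), the rate that matters is p/2. At 1% this gives 1 − 0.995^20 = 9.5%; at 5% it gives 1 − 0.975^20 = 39.7%.

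**5. What does not change?**

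- The any-AE rows: the event is counted either way.
- The Grade 3 non-serious rows: SAEs are excluded by definition.
- The individual solicited tables: these come from the eDiary.
- The SAE tables by preferred term: these have no local or general split.

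**The case against.** A reader might infer that every serious injection-site reaction disappears from the local counts. The documents do not support that. Solicited local reactions on Days 1–7 must go into the eDiary whatever their intensity and are counted from it, so a diary-recorded reaction keeps its local record. A reader might also infer from holding rule 1c that any injection-site necrosis would be counted as general. That is so only if it meets the SAE definition in Protocol 12.5.2; non-serious necrosis goes to the non-serious AE section, which the rule does not touch.

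The strongest defence goes further. The rule is pre-specified, explained and standard for the sponsor. The analyses are descriptive and no test depends on the split. No endpoint listed in SAP section 2 is itself a combined local and general count. SAEs are tabulated by preferred term and described in detail, and rule 1c is applied by the investigator on a single case without these tables. A serious reaction would be neither hidden nor delayed as a signal.

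All of this stands, and it keeps the point minor. It does not justify putting a known injection-site event in the general row when its coded term already identifies the site.

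One practical caution also stands. SAP 5.4.2.3 codes solicited redness to plain Erythema, which names no site, so preferred terms alone will not settle every case.

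**Conclusion.** The point holds in a limited form. A serious injection-site reaction known only from the expedited report is left out of the local rows and added to the general rows of the combined table, contrary to the protocol's description of that table and without an entry in SAP section 8. For a reaction also in the eDiary, the SAP leaves open whether it counts once or in both rows.

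The size is at most 5 percentage points per affected subject in a group of 20, and only where that subject has no other qualifying local record in the cell. How often this happens rests on an event rate that the documents do not give; such events are probably rare. This is an inexpensive improvement to a primary-method summary. It does not threaten the primary objective or safety oversight.

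**What to change.** Amend SAP 10.1.3.6 as follows:

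1. Count an SAE as local when its MedDRA preferred term is an injection- or administration-site term. Keep all other SAEs as general.
2. Settle ambiguous terms, for example plain Erythema, from the SAE narrative before the statistician is unblinded for the Day 91 analysis. The table covers at most 30 days after each dose, so the SAEs concerned have started by then.
3. Count an eDiary record and an SAE record of the same reaction once, as local.

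Preferred terms are already assigned for the SAE tables in SAP 5.4.1, so no new data, visit or CRF change is needed. The cost is a short SAP amendment, a small departure from the sponsor's standard counting rule, and a brief check of the few SAEs concerned.
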